12.4 Color Vision

The three color vision deficits are deutan, protan, and tritan. The degree of severity of color vision deficit is graded as normal, mild, moderate, or severe. The severity of color vision abnormality will be assigned to the highest degree of severity of the 3 color vision deficits. For example, the severities of deutan, protan, and tritan are mild, moderate, normal, respectively, for one of the eyes. For this case, moderate will be assigned as the highest level of severity for color vision abnormality.

The highest level of severity of color vision abnormality of left and right eyes at the given time point will be selected for the analysis. The frequency and proportion of participants for each level of the severity of color vision abnormality at baseline, Days 1, 4, 7, 10, 14, 15, Days 1-15 combined (i.e. worst color vision abnormality at any Days 1-15), 28, 42, and Days 28-42 combined (i.e. worst color vision abnormality at any Days 28-42) will be summarized by treatment group. For the by-time point summary, the denominator for the proportion is the number of participants with visual acuity assessment at the given time point.

The frequency and proportion of participants for each level of the severity of color vision abnormality at baseline that transitioned to a level of the severity of color vision abnormality at Days 1, 4, 7, 10, 14, 15, Days 1-15 combined (i.e. worst color vision abnormality at any Days

1-15), 28, 42, and Days 28-42 combined (i.e. worst color vision abnormality at any Days 28-42) will be provided by treatment group. For the by-time point summary, the denominator for the proportion is the number of participants with non-missing values at baseline and the given post-baseline time point.

Additionally, the transition of levels of severity of color vision abnormality from Days 1-15 combined to Days 28-42 combined will be summarized similarly as described above.

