
 Frequency of participants with any new (vs. baseline) eye symptom in one or both eyes. Mean and frequency distribution of duration (hours) of each eye symptom. Mean and frequency distribution of percentage of days with any eye symptom and each of the eye symptoms. 	The incidence of new eye symptoms, mean and frequency distribution of duration of each eye symptom, and mean and frequency distribution of percentage of days with any eye symptom and each of the eye symptoms will be summarized by treatment group.

 Mean/median change in visual acuity from screening (s) to lowest score during Days 1-15. Frequency of participants with any new color vision abnormalities (tritan, protan, deutan) in one or both eyes and degree of severity (mild, moderate, severe) 	Mean and median changes in visual acuity from screening to lowest score will be summarized by treatment group. Frequency of participants with any new color vision abnormalities, as well as the specific type of abnormality (tritan, protan, deutan) will be summarized by the number of eyes the abnormality occurs in (one or both), severity (mild, moderate, severe) and treatment group.

 Mean and frequency distribution of changes from Day 1 to 15 in HR, systolic blood pressure (SBP) and DBP as measured by the following 2 (BP) or 3 (HR) methods: 
 manual (vital signs), after at least 10 minutes in supine position (“manual, supine”); manual, after 2 (± 0.5) minutes in standing position (“manual, 2-min standing”); HR from ECG, supine position (“ECG, supine”) Frequency of participants with $\ge 25\%$ increase in HR, decrease in SBP, decrease 	Mean and frequency distribution of changes from Day 1 through Day 15 in HR, SBP and DBP will be provided by treatment group and by each method measured. The frequency of participants with $\ge 25\%$ increase in HR, decrease in SBP, decrease in DBP vs. baseline as measured with any of the methods will be provided by treatment group. The mean and frequency distribution of percentage of days with $\ge 25\%$ increase in HR, decrease in SBP, decrease in DBP vs. baseline will be provided by treatment group. The mean and median RR, QRS, QT, QTcF values from ECG will be provided by treatment group.

Endpoint	Statistical Analysis

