	
 Mean/median changes in visual acuity score from Screening to lowest score during Days 1-15. Frequency of participants with any new color vision abnormalities (tritan, protan, deutan) in one or both eyes and degree of severity (mild, moderate, severe).
Assess the impact on heart rate (HR), blood pressure (BP) and electrocardiogram (ECG) profile of each dose regimen of TBA-7371 and of HRZE over the 14-day treatment period.	
From Day 1 through Day 15:
 
 Mean and frequency distribution of changes in heart rate (HR), systolic blood pressure (SBP) and diastolic blood pressure (DBP) as measured by the following 2 (BP) or 3 (HR) methods: 
 Manual HR, SBP and DBP from vital signs, after at least 1 minute in supine position (“manual, supine”); Manual HR, SBP and DBP from vital signs, after 2 (± 0.5) minutes in standing position (“manual, 2-minute standing”); HR from ECG, supine position (“ECG, supine”) Frequency of participants with $\geq 25\%$ increase in HR, decrease in SBP, decrease in DBP vs. baseline as measured with any of the methods described above. Mean and frequency distribution of percentage of days with $\geq 25\%$ increase in HR, decrease in SBP, decrease in DBP vs. baseline. 
Mean/median change from Screening through Day 15 in PR, RR, QRS, QT, and QTcF interval values from baseline ECG.

Assess whether there is tachyphylaxis over the 14-day treatment period for HR, SBP, DBP and eye symptoms	
 Mean change in HR, SBP, and DBP from Day 1 to Days 4, 7, 10, 14, and 15 for each of 2 BP and 3 HR measurement methods described above. Change in frequency of participants with eye symptoms (all, severe, serious) and change in worst visual acuity score and frequency of color vision abnormalities (tritan, protan, deutan) in one or both eyes and degree of severity (mild, moderate, and severe) from Day 1 to Days 4, 7, 10, 14, and 15.
Assess whether cardiovascular and/or ophthalmic adverse events persist or recur up to 4 weeks after discontinuation of treatment with TBA-7371.	
 Mean change in HR, SBP, and DBP from Baseline to Days 28 and 42 and from Day 14 to Days 28 and 42 as measured by the following 2 (BP) or 3 (HR) methods: 
 Manual HR, SBP and DBP from vital signs, after at least 10 minutes in supine position (“manual, supine”);

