8 CHANGES IN CONDUCT / RE-LANNED ANALYSES FROM THE PROTOCOL

No changes have been made to the planned analyses.

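### SAP 12.4 omits the breakdown of new colour vision abnormalities by type and number of eyes that Protocol Table 9 specifies, and one of its tables uses the visual acuity denominator

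*SAP*

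**What the plan says.** **Endpoint.** SAP Section 5.2 (Table 2) states the secondary safety endpoint over Days 1 to 15 as "Frequency of participants with any new color vision abnormalities (tritan, protan, deutan) in one or both eyes and degree of severity (mild, moderate, severe"). Protocol Tables 2 and 6 carry the same endpoint.

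**Protocol analysis.** In Protocol Table 9 (Section 9.4) the analysis column gives any new abnormality, "as well as the specific type of abnormality (tritan, protan, deutan) will be summarized by the number of eyes the abnormality occurs in", with severity and treatment group as the further breakdowns. The same analysis text stands against three rows: new abnormalities in Days 1 to 15, change from Day 1 during treatment, and persistence to Days 28 and 42.

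**SAP analysis.** SAP Section 12.4 first takes the worst of the three deficits: "The severity of color vision abnormality will be assigned to the highest degree of severity of the 3 color vision deficits". It then takes the worse eye: "The highest level of severity of color vision abnormality of left and right eyes at the given time point will be selected for the analysis". Three summaries follow, all built on that single grade:

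- the distribution of grades at each time point;
- transitions from baseline to each time point;
- transitions from Days 1-15 combined to Days 28-42 combined.

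**Denominators in 12.4.** For the by-time-point distribution, "the denominator for the proportion is the number of participants with visual acuity assessment at the given time point". For the baseline transitions, "the denominator for the proportion is the number of participants with non-missing values at baseline and the given post-baseline time point".

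**Declared changes.** SAP Section 8: "No changes have been made to the planned analyses".

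**The concern.** Altered colour vision is a known signal for this drug. Protocol Section 2.3 lists it among the most common treatment-emergent events in the healthy volunteer trial, with dose-related frequency. It adds that eye symptoms appeared to track Cmax, which is the reason for the divided-dose regimens. The protocol therefore asked which type of deficit appears and whether one or both eyes are affected, and the test is done on each eye (Protocol 8.3.7). A summary that keeps only the worst grade cannot show whether regimens differ in either respect. A mild tritan deficit in both eyes and a mild deutan deficit in one eye would fall in the same row.

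The denominator is a second, smaller matter. The colour vision proportion is divided by a count from a different test, in a sentence identical to the one in SAP 12.3 for visual acuity. It was probably carried over.

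**Working it through.** The documents give no figure to reproduce. The check is what the worst-grade rule keeps, and what the denominator does at the planned group size.

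**1. What the single grade retains.** There are three types in two eyes, each graded normal, mild, moderate or severe (SAP 12.4), so a participant has 6 gradings per visit and 4^6 = 4,096 possible patterns. The rule maps these to four values:

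| Worst grade | Patterns |
|---|---|
| Normal | 1 |
| Mild | 2^6 − 1 = 63 |
| Moderate | 3^6 − 2^6 = 729 − 64 = 665 |
| Severe | 4^6 − 3^6 = 4,096 − 729 = 3,367 |

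Each type can be present in no eye, one eye or both, which gives 3^3 − 1 = 26 non-empty combinations of type and number of eyes. Enumeration shows that all 26 are compatible with each of mild, moderate and severe. Type and number of eyes therefore cannot be recovered from any table in 12.4.

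**2. What the transition table still gives.** For a participant normal in all 6 gradings at baseline, the worst grade rises above normal exactly when at least one grading becomes abnormal; this holds for all 4,096 patterns. The move from normal to mild, moderate or severe over Days 1-15 combined is therefore any new abnormality in at least one eye, by worst severity. Colour vision deficiency now or in the last 5 years is exclusion criterion 4b (Protocol 5.2), and the screening eye assessment is used for eligibility (Protocol 8.3.7). Baseline should nearly always be normal.

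**3. What it misses if baseline is abnormal.** Take mild deutan in one eye at baseline, persisting. A new mild deficit in one or more of the other 5 gradings can arise in 2^5 − 1 = 31 ways. In all 31 the worst grade stays mild, so no transition is recorded.

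**4. Elsewhere in the SAP.** Section 10.2 summarises colour vision deficiency in one or both eyes at baseline. No section tabulates type or number of eyes after baseline.

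**5. Denominator.** Planned group size is 15 per TBA-7371 regimen (SAP 6.1). The documents do not say how many participants will have an acuity test without a colour test. Assuming 0, 1 or 2 of 15:

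| Acuity but no colour test | 1 event, as written | 1 event, colour denominator | 3 events, as written | 3 events, colour denominator |
|---|---|---|---|---|
| 0 | 1/15 = 6.7% | 1/15 = 6.7% | 3/15 = 20.0% | 3/15 = 20.0% |
| 1 | 6.7% | 1/14 = 7.1% | 20.0% | 3/14 = 21.4% |
| 2 | 6.7% | 1/13 = 7.7% | 20.0% | 3/13 = 23.1% |

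The transition table is unaffected, because it counts participants with values at both time points.

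**The case against.** A reader might infer that the stated endpoint is not produced at all. The documents do not support that. In the endpoint, the reference to one or both eyes can mean at least one eye; the eye symptom endpoint uses the same phrase. On that reading the transition table delivers the endpoint for almost everyone. Protocol Section 9.4.2.2 also describes the colour vision analysis with no split by type or eye. The split rests on the analysis column of Table 9.

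Nor are type and eye hidden altogether. SAP 9.1 lists all measured variables individually, which is readable at about 15 per group. Protocol 8.3.7 requires clinically meaningful colour test findings to be recorded as adverse events, and SAP 12.2 tabulates eye symptom-related events by preferred term.

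On the denominator, one might infer that every colour vision proportion is wrong, or that any missing colour test lowers it. Neither holds. Only the by-time-point table is affected, and only when acuity was tested and colour vision was not. Both tests belong to one set of procedures on each eye assessment day, and nothing in the documents suggests unequal completeness.

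Finally, the summary is descriptive, with no test or decision rule, and the SAP history for Amendment 1 records that the colour vision analyses were revised.

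All of this limits the point but does not remove it. Table 9 is explicit that results are "summarized by the number of eyes the abnormality occurs in (one or both), severity (mild, moderate, severe) and treatment group", and for each specific type. Listings do not replace a frequency table. The Amendment 1 entry does not say that a protocol-specified breakdown was dropped, and Section 8 says that nothing changed. Colour vision is always tested after acuity (Protocol 8.3.7), so an interrupted session would leave exactly the pattern that makes the denominator wrong.

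**Conclusion.** The point holds in limited form. SAP 12.4 omits a breakdown by type and by one versus both eyes that Protocol Table 9 specifies against three rows, and Section 8 does not declare the departure. Missing from the summary tables are type, one versus both eyes, and new deficits of the same or lower grade in anyone abnormal at baseline. Any new abnormality by worst severity remains available for participants normal at baseline; that they are nearly all rests on criterion 4b being applied as written.

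The denominator is a separate and small textual error in one table. Under the assumption of 1 or 2 of 15 with acuity but no colour test, 3 events read 20.0% instead of 21.4% or 23.1%; with equal completeness the error is zero. It has no bearing on whether the endpoint can be obtained.

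No hypothesis test, sample size or success criterion is affected. It is still worth correcting, because it concerns a known safety signal and the data are already collected.

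**What to change.** 1. Add to SAP 12.4 a table of participants with a new abnormality (absent at screening) by type, one or both eyes, severity and treatment group, at each time point and for Days 1-15 and Days 28-42 combined. Define new at the level of type and eye, so that a participant abnormal at screening can still contribute a new deficit.
2. In the by-time-point table, replace the denominator with participants who have a colour vision assessment at that time point.
3. Keep the worst-grade and transition tables as they are.
4. If the breakdown is not wanted, state the departure from Protocol Table 9 and the reason in SAP Section 8.

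The cost is one table from data already collected per eye, and one corrected sentence. No new data collection is needed.

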12.5 Vital Signs

12.5.1 Intraday Vital Signs Results

Intraday values of vital signs (HR, SBP, and DBP) measured while in supine and while in standing at predose, and 2.5h, 10.5h, and 16.5h after the time of 1st daily dose of study drug on Days 1, 4, 7, 10, and 14 and changes from predose taken on the same day will be summarized using descriptive statistics by treatment group. Line plots of mean of intraday HR, SBP, and DBP measured while in supine and while in standing by treatment group will be provided.

Potentially clinically important criteria of intraday changes from presdose in HR, SBP, and DBP while measured in supine and while in standing are defined as follows:

- $\geq 25\%$ increase in supine HR
- $\geq 25\%$ increase in standing HR
- $\geq 25\%$ decrease in supine SBP
- $\geq 25\%$ decrease in standing SBP
- $\geq 25\%$ decrease in supine DBP
- $\geq 25\%$ decrease in standing DBP

For each of the criteria, the frequency and proportion (expressed in percent) of participants who met the criterion at each time point will be provided by treatment group. For the by-time point summary, the denominator for the proportion is the number of participants in the treatment group with non-missing values at predose and the given post-predose time point taken on the same day.

12.5.2 Daily Vital Signs Results

Daily values of vital signs (HR, SBP, and DBP) measured while in supine and while in standing at baseline (Day 1 predose), Days 2 (predose), 3, 4 (predose), 5, 6, 7 (predose), 8, 9, 10 (predose), 11, 12, 13, 14 (predose), 15, 28, and 42 and changes from baseline will be summarized by treatment group using descriptive statistics. Line plots of mean of daily HR, SBP, and DBP measured while in supine and while in standing by treatment group will be provided.

Potentially clinically important criteria for changes from baseline in HR, SBP, and DBP while measured in supine and while in standing are defined as follows:

- $\geq 25\%$ increase in supine HR

- $\geq 25\%$ increase in standing HR
- $\geq 25\%$ decrease in supine SBP
- $\geq 25\%$ decrease in standing SBP
- $\geq 25\%$ decrease in supine DBP
- $\geq 25\%$ decrease in standing DBP

For each of the criteria, the frequency and proportion (expressed in percent) of participants who met the criterion at each time point will be provided by treatment group. For the by-time point summary, the denominator for the proportion is the number of participants in the treatment group with non-missing values at baseline and the given post-baseline time point.

For each of the criteria, any day that a participant whose vital signs results met the criterion will be counted toward the number of days with the criterion met in the study for that individual. Number of days with the criterion met will be summarized by treatment group using descriptive statistics.

Additionally, categorical number of days with the criterion met will be summarized by treatment group as follows:

- 1-3 days
- 4-6 days
- 7-9 days
- 10-12 days
- 13-15 days
- ≥ 16 days

The summary will include the frequency and proportion (expressed in percent) of participants for each category. For computing proportions, the denominator will be the number of participants in the treatment group who met the respective criterion.

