5. **Blood/serum sample collection for clinical safety laboratory assessment.** The Day 3 and 7 sampling will occur before the 1st dose of study drug.
6. **Urine sample collection drug screening:** cannabinoids, cocaine, amphetamines, opiates, methamphetamines.
7. **Overnight sputum collection for eligibility assessment.** Sputum assessment, including volume, will be performed by a Sponsor-approved central laboratory (see laboratory study instruction document). The 1st of the 3 overnight sputum collections (Day -7 to Day -3) conducted during the Screening Period will be used to assess eligibility as follows: sputum volume (must be at least 10 mL), acid-fast bacilli detection, *Mycobacterium tuberculosis* (Mtb) positivity and rifampicin sensitivity via the GeneXpert® diagnostic system (Cepheid). In case inclusion criteria cannot be met from the 1st overnight sputum collection, one or more of the above procedures can be conducted on a 2nd overnight sputum collected during the Day -7 to -3 screening period if the patient is domiciled at the site for both.
8. **Vital sign and body weight recording.** The following 5 vital signs will be recorded: axillary body temperature (BT), respiratory rate (RR), heart rate (HR), systolic blood pressure, (SBP), diastolic blood pressure (DBP). Body weight (BW) will also be recorded with vital signs. Vital signs and body weight will be recorded as follows:
 - Screening Phase: vital signs and BW once in the morning at approximately the same time the 1st daily dose study drug will be administered. SBP, DBP and HR can be repeated twice if exclusion criteria are met.
 - Study Treatment Phase: vital signs and BW once every morning (Days 1 to 14) before administration of the 1st daily dose of study drug; in addition, on Days 1, 4, 7, 10 and 14 vital signs will also be collected 2.5h, 10.5h and 16.5h after the time of 1st daily dose of study drug (see Table 4).
 - Follow-up Phase: vital signs and BW on Day 15 in the morning before 1st daily dose of SoC medication; on Days 28 and 42 during the visit.

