	
Frequency of participants with any new (vs. Screening) eye symptom in one or both eyes.Mean and frequency distribution of duration (hours) of each eye symptom.Mean and frequency distribution of percentage of days with any eye symptom and each of the eye symptoms.Mean/median change in visual acuity score from Screening to lowest score during Days 1-15.Frequency of participants with any new color vision abnormalities (tritan, protan, deutan) in one or both eyes and degree of severity (mild, moderate, severe). 
Heart rate (HR) and blood pressure (BP) from Day 1 through Day 15:
 
Mean and frequency distribution of changes in HR, SBP and DBP as measured by the following 2 (BP) or 3 (HR) methods:
Manual HR, SBP and DBP from vital signs, after at least 10 minutes in supine position (“manual, supine”);Manual HR, SBP and DBP from vital signs, after 2 (± 0.5) minutes in standing position (“manual, 2-min standing”);HR from ECG, supine position (“ECG, supine”)Frequency of participants with $\geq 25\%$ increase in HR, decrease in SBP, decrease in DBP vs. baseline as measured with any of the methods described above.Mean and frequency distribution of percentage of days with $\geq 25\%$ increase in HR, decrease in SBP, decrease in DBP vs. baseline.Mean/median change from screening through day 15 in RR, PR, QRS, QT, QTcF values from baseline ECG. 
Tachyphylaxis over the 14-day treatment period for HR, SBP, DBP and eye symptoms:
 
Mean change in HR, SBP and DBP from Baseline (Day 1, pre-dose) to Days 4, 7, 10, 14, and 15 for each of the 2 BP and 3 HR measurement methods described above.Change in frequency of participants with eye symptoms (all, severe, serious) and change in worst visual acuity score and frequency of color vision changes from Day 1 to Days 4, 7, 10, 14 and 15. 
Cardiovascular and/or ophthalmic AEs persistence or recurrence up to 4 weeks after discontinuation of treatment with TBA-7371:
 
Mean change in HR, SBP and DBP from Baseline (Day 1, pre-dose) to Days 28 and 42 and from Day 14 to Days 28 and 42 for each of the following measurement methods:
--	---

Table 4. Safety Endpoint

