9.2 Definitions

Screening EBA Measure: Average of the EBA measurements (i.e., log CFU, TTP in MGIT, and log concentration of sputum LAM) from the day -2 and day -1 overnight sputum samples of the screening phase will be used to determine the screening EBA measurement. If one of the overnight sputum samples is missing, the single non-missing sample will be directly used as the screening EBA measurement.

Baseline definition for other efficacy and safety variables: The last assessment made prior to the first administered dose of study intervention will be considered baseline for analysis purposes. Baseline values of ECG and vital signs are measured on Day 1 before the first dose of study medication is administered.

Day 1: Study day 1 is the day of first administration of TBA-7371 or HRZE. Positive study days will be counted forward from Day 1. Day -1 will be the date immediately preceding Day 1, and negative study days will be counted backward from Day 1.

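### The baseline-referenced 25% criteria and day count for heart rate and blood pressure use only pre-dose readings during treatment, so two protocol secondary safety endpoints are not delivered as written

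*SAP*

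**What the plan says.** **Endpoint.** Protocol 3.2 (Table 6) and SAP 6.4 (Table 4) define two measures for Day 1 through Day 15. One is the frequency of participants with a rise in HR, or a fall in systolic or diastolic pressure, of 25% or more "vs. baseline as measured with any of the methods described above". The other is the mean and distribution of the percentage of days with such a change. The methods are supine and standing vital signs and, for HR, the supine ECG. Neither measure is restricted to pre-dose values. Protocol 8.3.6 adds that changes of this size found on ECG contribute to the secondary endpoints.

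**Schedule.** Protocol 1.3, footnote 8, takes "vital signs and BW once every morning (Days 1 to 14) before administration of the 1st daily dose of study drug". Three further sets a day are planned on five of those days, timed from the morning dose: "on Days 1, 4, 7, 10 and 14 vital signs will also be collected 2.5h, 10.5h and 16.5h after" that dose.

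**Baseline.** SAP 9.2: "Baseline values of ECG and vital signs are measured on Day 1 before the first dose of study medication is administered".

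**Daily analysis.** SAP 12.5.2 lists its values "at baseline (Day 1 predose), Days 2 (predose), 3, 4 (predose), 5, 6, 7 (predose), 8, 9, 10 (predose), 11, 12, 13, 14 (predose" and continues with Days 15, 28 and 42. It then sets "Potentially clinically important criteria for changes from baseline in HR, SBP, and DBP" at 25% and counts days: "any day that a participant whose vital signs results met the criterion will be counted toward the number of days with the criterion met".

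**Intraday analysis.** SAP 12.5.1 applies the same 25% cut-offs at 2.5, 10.5 and 16.5 h, by time point, to the change from that day's pre-dose value. It has no day count.

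**ECG.** SAP 12.6 summarises ECG heart rate but sets threshold criteria only for QTcF.

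**Changes.** SAP section 8 declares no change to the planned analyses.

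**The concern.** In the phase 1 study a heart rate increase with a fall in blood pressure was among the most common treatment-emergent events and was dose related (Protocol 2.3). The BID and TID regimens are included to show what splitting the daily dose does to activity and tolerability (Protocol 4.3). A count of days with a 25% change is therefore likely to be read across regimens.

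If that count sees only the reading taken just before the next dose, a change that comes and goes after dosing is not counted. If the post-dose readings are judged against a different reference, they do not fill the gap. The time since the last dose at the pre-dose reading also differs by regimen, so the comparison is not made at equal times.

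**Working it through.** The plan states no figure for this point, so there is none to reproduce. The check compares the schedule with the SAP rules, then runs one sensitivity calculation on assumed pharmacokinetics.

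**1. Readings that feed the day count.** The listed values for Days 2, 4, 7, 10 and 14 are marked as pre-dose. The unmarked treatment days have only the morning pre-dose reading, by schedule. Per position (supine or standing), Days 1-14:

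- pre-dose: 14, of which Day 1 is the baseline, leaving 13;
- post-dose: 5 days × 3 = 15;
- post-baseline total: 13 + 15 = 28; listed in 12.5.2: 13, with no post-dose reading.

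**2. What the same-day reference does.** Let B be baseline, P the same-day pre-dose value and R a post-dose value. For HR, 12.5.1 needs R ≥ 1.25P. If P = (1 + a)B, this is R ≥ 1.25(1 + a)B, a rise over baseline of 0.25 + 1.25a. For BP, R ≤ 0.75P with P = (1 − b)B requires a fall of 0.25 + 0.75b. On Day 1, a = b = 0 and the two references agree. On Days 4, 7, 10 and 14, any residual effect at pre-dose (a or b between 0 and 0.25) leaves a band of post-dose values that meet the protocol endpoint but neither SAP criterion. If the pre-dose value has moved the other way, 12.5.1 instead counts changes smaller than 25% from baseline.

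**3. Endpoint against SAP output.**

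| Protocol endpoint | SAP |
|---|---|
| Participants, any method, vs baseline, Days 1-15 | Proportions by time point and position. The number meeting each 12.5.2 criterion appears only as the denominator of the day categories, per position and on the listed readings |
| Percentage of days, Days 1-15 | Number of days. Days 28 and 42 are listed and not excluded |
| ECG as third HR method | No 25% criterion |

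The listed post-baseline days number 14 (Days 2-15) + 2 = 16. The top category, 16 days or more, can be reached only if Days 28 and 42 both count.

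**4. Time since last dose.** Dose times (Protocol 1.1.7) are 0 h (QD), 0 and 12 h (BID), and 0, 7 and 14 h (TID). At the next pre-dose reading: 24 − 0 = 24 h, 24 − 12 = 12 h, 24 − 14 = 10 h. At the 2.5, 10.5 and 16.5 h readings: QD 2.5, 10.5, 16.5 h; BID 2.5, 10.5, 4.5 h; TID 2.5, 3.5, 2.5 h.

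**5. Sensitivity.** The documents give no half-life. Assumed: one compartment, first-order absorption at 2/h, superposition to Day 14, with each dose D contributing D·ka/(ka − ke)·(e^(−ke·s) − e^(−ka·s)), where s is the time since that dose and ke = ln 2 / half-life. Levels are in arbitrary units.

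| Half-life | Pre-dose/peak QD, BID, TID | Pre-dose level 200 QD vs 100 BID | Pre-dose level 400 QD vs 100 TID |
|---|---|---|---|
| 1.5 h | 0%, 0.8%, 2% | 0.00 vs 0.51 | 0.01 vs 1.33 |
| 3 h | 0.6%, 9%, 14% | 0.89 vs 7.54 | 1.77 vs 13.94 |
| 6 h | 8%, 31%, 38% | 14.15 vs 35.38 | 28.30 vs 58.62 |
| 12 h | 28%, 56%, 62% | 68.65 vs 102.97 | 137.30 vs 162.81 |
| 24 h | 53%, 75%, 79% | 202.91 vs 244.93 | 405.81 vs 377.64 |

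In both pairs the QD regimen has the higher peak at every half-life tried. Its pre-dose level is lower throughout for 200 mg QD against 100 mg BID, but for 400 mg QD against 100 mg TID only up to 12 h; at 24 h the order reverses.

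**The case against.** A reader might infer that the plan misses the peak effect. It does not. SAP 12.5.1 reports changes of 25% or more at three post-dose times on five days, supine and standing. SAP 12.6.1 summarises ECG heart rate at the same times, and 12.5.3 covers orthostatic changes there. Adverse events of Grade 2 or above, or serious, related to a HR rise or BP fall are of special interest, and the IDMC reviews vital signs. Nor are post-dose readings never compared with baseline: on Day 1 the same-day pre-dose value is the baseline. Both points stand and limit the gap to the baseline-referenced criteria and day count, from Day 4 onward for the post-dose readings.

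The counting sentence itself speaks of vital signs results and does not expressly exclude post-dose values. That is true, but the sentence follows a list with no post-dose time. SAP 12.5.3 names the post-dose times before its own day count, which suggests the omission in 12.5.2 is meaningful. At best the text lets two programmers derive different counts.

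Morning-to-morning comparison removes time-of-day variation and is worth keeping. Part of the limit is the schedule: 9 of 14 treatment days have no post-dose reading, and no analysis can recover one. The endpoint is secondary and descriptive, and all values are to be listed, so the count could be rebuilt later. These points lower the weight of the finding but do not make the SAP match the endpoint.

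**Conclusion.** The point holds in this form. Read with its own list of time points, SAP 12.5.2 bases its treatment-phase criteria and day count on pre-dose readings. From Day 4 no post-dose vital sign is tested against baseline, and ECG heart rate is not tested against the 25% cut-off at all. The any-method participant frequency and the percentage of days are therefore not delivered as the protocol defines them, while SAP section 8 reports no change. The size that can be stated from the documents is 13 of 28 post-baseline readings per position, and 0 of 5 days with their post-dose readings in the count.

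It is tempting to conclude that QD regimens will look safer than BID or TID. The 24, 12 and 10 h gaps make an uneven comparison possible, but the documents do not fix its direction or size. They give no half-life and no exposure-effect relation for HR or BP. The link to Cmax is drawn for eye symptoms, and phase 1 suggested tachyphylaxis for HR and BP. Under the assumed model, a very short half-life leaves almost nothing at pre-dose in any regimen, and a 24 h half-life reverses one of the two comparisons. It is a risk to guard against, not a demonstrated bias.

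**What to change.** In SAP 12.5.2 and 12.6:

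1. Add the number and proportion of participants with any scheduled reading from Day 1 through Day 15, pre-dose or post-dose, that shows a HR rise or BP fall of 25% or more from the Day 1 pre-dose baseline. Include supine, standing and, for HR, ECG values, and show the result combined and by method.
2. Add a percentage-of-days summary using all readings against baseline, with Days 1, 4, 7, 10 and 14 as its denominator.
3. Keep the pre-dose daily summary as a separate, labelled table, limited to Days 1-15 for this endpoint.

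The cost is SAP wording and a derived variable; every reading is already collected. There are two drawbacks. More readings give more chance crossings of the threshold: with four times and three methods, HR has up to 12 readings on an intensive day. The new percentage describes 5 of 14 treatment days. Showing it beside the pre-dose table makes both limits visible.
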